#### **4.2 Research Assistant Training and Field Testing of Procedures and Equipment**

Before the RCT is started, the procedures and equipment (including the TLC-WALK and health education control systems) will be refined and undergo final testing. This setup phase will include developing a detailed manual of operations, training study staff, interviewing subjects, implementing measurement techniques, and

collecting data. The study coordinator will organize, schedule, and oversee the completion of all training sessions. The importance of strict adherence to the manual of operations will be emphasized repeatedly during training sessions. An initial session will include the appropriate expert members of the study team to ensure that appropriate techniques are demonstrated to all research staff. Data collected during the staff training will be analyzed for quality purposes by the appropriate study team members. Minor refinements to the two intervention systems will also be made during this period.

#### **4.3 Participants for the Randomized, Controlled Trial**

We will recruit 160 patients with PD-MCI into our study. We will identify eligible patients with PD through review of electronic medical records. Specifically, this approach will involve identifying patients in VISN 1 with the following inclusion criteria: 40 years of age or older, an ICD-9 code for PD, at least 2 of the 3 cardinal signs of PD (resting tremor, rigidity, bradykinesia), response to dopaminergic medication, and MCI based on Movement Disorder Society Task Force criteria for MCI in PD (Petersen, 2004). Patients who have angina pectoris (unless symptomatically resolved post-revascularization), a history of myocardial infarction (MI) within 6 months, or a history of ventricular dysrhythmia requiring current therapy will be excluded from consideration.

To access electronic medical records we will use the CAPRI system which provides one interface into the Vista systems within VISN 1. We will review these data to confirm specific eligibility criteria. Patients with PD typically have an initial Neurology consultation and then are seen in Neurology Clinic every 6 months. A standardized VA note format is utilized which includes HPI, medications, and detailed neurologic examination at each visit. The initial VA Neurology consultation will be reviewed with as many subsequent clinic notes as needed to establish the diagnosis of PD and responsiveness to dopaminergic therapy. The two most recent Neurology Clinic notes will also be reviewed to determine current medication use and functional status. Also, Primary Care provider notes and any hospital discharge summaries from the previous year will be reviewed for evidence of exclusionary conditions.

##### **4.3.1 Randomization**

All subjects are recruited with the understanding that they will be randomized to one of two groups: one group will be assigned to use the TLC-WALK system (see Section 4.4.1) and the other group will use the health education control TLC system (see Section 4.4.2). A staff member will be in charge of the randomization and all the tasks related to group assignment. At the conclusion of the baseline visit, half of the 160 subjects will be randomized to each experimental arm with a computer-based algorithm for group assignment, which cannot be modified once the inclusion parameters are specified for a given subject.

#### **4.4 The Study Interventions**

The study interventions represent a modification of the walking exercise and control interventions of Lautenschlager et al. (2008) (see Section 2.5.2 above). Our interventions will be remotely delivered via smartphone and will take place during an 18-month period of follow-up. Subjects who are randomized will have the appropriate remote connection system made available to them and will be instructed on how to use the system. All equipment and instruction manuals will be given to the subjects at the conclusion of the baseline visit.

##### **4.4.1 TLC-WALK Intervention**

Subjects assigned to receive TLC-WALK will be instructed in the specific components of the home-based exercise program, including proper warm-up before exercise, effective walking technique as well as appropriate shoes and foot care, and issues of safety during exercise (Section 3.1). This will include a hands-on training session during which the subject will actually use the TLC-WALK system for his/her initial walking session under the guidance of a trained staff member. We will individualize guidance regarding the walking program to reduce patient-identified barriers to walking within each subject's specific community. This discussion will focus on opportunities to engage in walking in safe outdoor locations (minimal traffic, adequate crosswalks), at senior or community centers, local exercise facilities such as the YMCA, or large climate-controlled spaces such as malls. The staff member assigned to randomization and subject orientation will carry out the subject training.

Adherence to this intervention will be encouraged by intermittent newsletters, birthday cards, holiday

greeting cards, and certificates of study participation. Another method to promote adherence will be through the use of incentives (Robinson et al., 2007). We will provide participants with an incentive program to reward adherence to the training program. Participants will earn points toward prizes (e.g., key chains, mugs, hats, t-shirts, movie passes, gift cards) for completion of each session with bonus points awarded at the end of each week if no sessions were missed for that week. Participants will be given a list of all available prizes with their point value. Points can be cashed in at any time to claim a prize.

#### **4.4.2 Health Education Control**

Subjects randomized to the health education control group will participate in interactive health education sessions via smartphone. This health education control system provides general information about a variety of health topics including topics on stretching and aerobic conditioning exercise. Control subjects will be asked to complete a health education session three times a week with the initial session being done with a research assistant at the conclusion of the baseline examination. The delivery of this content makes use of both the audio and video capabilities of the smartphone technology. Voice content is overlaid on background music and supplemented by still and video images to enhance the educational value of the presentation. There are opportunities for subject interaction, e.g., the ability to request additional information within the content area.

During the first three weeks of the intervention, instructions for exercise based on the Fitness Counts program developed by the National Parkinson Foundation (Cianci, 2006) are sequentially presented to the participant. There are a total of six topics (three related to stretching and three related to aerobic conditioning exercise) in this content area. Subsequently, during each session, participants will select a topic from four content areas: common symptoms, medical conditions, preventive medicine topics, and tips for healthy living with PD. These PD-specific tips include mobility strategies, such as strategies for moving from lying down to a sitting position, and from sitting to standing position, and tips to help with performance of daily activities including organization of the physical environment and reducing time pressure. Control patients will also receive an illustrated booklet demonstrating these strategies and tips.

The health information dialogues were developed to allow users to identify subtopics about which they desire more information while skipping others of less interest. The dialogues avoid long stretches of uninterrupted talking by the system. Topics already viewed will be removed from the list at subsequent calls (although they can be located by choosing “previously viewed topics”) except for the six topics based on the Fitness Counts program. These six topics will remain on the list.

Health education sessions will be scheduled in advance. At enrollment, subjects will indicate their weekly preferred days and times to complete the sessions. This information will be used in a similar fashion to the TLC-WALK application to determine the next scheduled session and to initiate each session at the scheduled time if not already completed.

A similar approach as described above (see Section 4.4.1) will be used in the control group to encourage and maintain study participation including an incentive program that gives subjects points for completing sessions which can be used towards prizes.

#### **4.5 Outcome Data Collection**

We will assess the ADAS-Cog (Rosen et al., 1984) at baseline, 6 months, 12 months, and 18 months at the Jamaica Plain campus of the VA Boston Healthcare System. This will be collected by a trained staff member who will be blinded to group assignment. The ADAS-Cog also was assessed as part of the physical activity intervention study of Lautenschlager et al. (2008). The scale consists of eleven items assessing memory, orientation, language, and praxis, with scores ranging from 0 (least impaired) to 70 (most impaired).

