**A Telemedicine Intervention to Improve Cognitive Function in Patients With PD**

**NCT02248649**

**July 2, 2015**

## PROTOCOL

### 1. SPECIFIC AIMS

Parkinson's disease (PD) is an age-related neurodegenerative disorder characterized by insidious onset. Characteristic features of PD include resting tremor, rigidity, bradykinesia, and postural instability/gait disturbance. PD also includes a spectrum of nonmotor symptoms. One of the most important and disabling of these symptoms is progressive cognitive impairment leading to dementia. The effects of nonpharmacological interventions on cognitive impairment in older adults at risk for Alzheimer's disease (AD) have been studied systematically, but additional data are needed to evaluate the effects of such interventions on cognitive impairment in PD (Hindle et al., 2013). Controlled trials in older individuals with cognitive impairment and in small samples of patients with PD have indicated a significant positive effect of physical activity on cognitive measures.

We propose to build on our experience with objective, physiologically-based measurements of physical activity in randomized, controlled trials (RCTs), to conduct an RCT of a home-based physical activity intervention program among patients with mild cognitive impairment (MCI) in PD (PD-MCI) – a group at high risk of experiencing further cognitive decline and most likely to benefit from physical exercise. We will test the effects of the intervention over 6 months on the Alzheimer Disease Assessment Scale-Cognitive Subscale (ADAS-Cog). We hypothesize that patients with PD-MCI in the intervention arm will have less decline in this outcome over 6 months compared with those in the control arm. Furthermore, we will test for the durability of the effect with a tapered physical activity dosage through 18 months of follow-up.

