### **2.5.2 Evidence that Physical Activity Affects Cognitive Decline**

A relatively substantial literature of observational epidemiological studies exists that explored the association between physical activity and AD. In this context, most prospective epidemiological studies of physical activity and subsequent AD have found a decreased risk of AD with higher levels of physical activity (Scarmeas et al., 2009; Yoshitake et al., 1995; Andel et al., 2008; Abbott et al., 2004; Larson et al., 2006; Laurin et al., 2001; Rovio et al., 2005; Podewils et al., 2005), although a few studies failed to find an association (Akbaraly et al., 2009; Ravaglia et al., 2008; Verghese et al., 2003). These studies all started with non-demented populations at baseline and followed participants for development of AD over a period of years, ranging from less than 4 to 31. A meta-analysis of nine of the cohort studies of physical activity and AD yielded a summary hazard ratio for AD with higher physical activity of 0.72 (95% CI, 0.53 to 0.98) (Daviglus et al., 2011). All of the studies used self-report of physical activity which lacks precision and, in turn, may underestimate the impact of exercise on cognitive decline. In support of this hypothesis, in a recent study (Buchman et al., 2012) using actigraphy to objectively measure physical activity in older adults, results revealed a significant hazard ratio of 0.477 (95% CI, 0.27 to 0.83) between daily physical activity and incident AD that exceeded the summary hazard ratio of 0.72 reported in the meta-analysis alluded to above (Daviglus et al., 2011).

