Subjects in the intervention group were asked to engage in 150 minutes of moderate physical activity per week, to be completed in three 50-minute sessions over a period of 6 months. Although subjects were allowed to choose from a variety of forms of exercise, almost all chose walking. Subjects in the usual care control group received educational material about managing memory loss, stress management, healthful diet, alcohol consumption, and smoking. The study revealed a significant positive effect of physical activity on a comprehensive cognitive measure (ADAS-Cog) and a delayed recall task. A limitation of this study was the inability to adequately monitor the progression of physical activity and encourage adherence by telephone as originally planned.

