### Significance

Progressive cognitive impairment leading to dementia is an important component of PD, contributing to significant levels of disability. The number of veterans who will develop PD and, in turn, the number of veterans with PD who are likely to develop dementia is likely to increase substantially (Dorsey et al., 2007). Given the profound negative health and social consequences associated with the development of dementia, it is critical to identify interventions that effectively slow the decline of cognitive function to prolong the time to onset of dementia.

Based on results of prior studies, physical activity is one of the few nonpharmacological interventions that holds promise in slowing cognitive decline. The benefits of a physical activity intervention for persons with PD may rival or exceed the benefits of pharmacologic interventions without the unwanted adverse effects. In addition, unlike medication, physical activity has broad benefits that are not confined to cognitive function. Studies in PD, for example, have revealed improvements in motor impairments, physical function, and QOL following exercise in the form of walking (Herman et al., 2007).

The proposed study uses rigorous methodology and builds on previous work in which a relationship between greater physical activity levels and less cognitive decline has been confirmed. Objective,

physiologically-based measures of physical activity will allow accurate representation of the duration and intensity of physical activity among subjects. Furthermore, these objective measures will be the basis for the progression and optimization of physical activity throughout the course of the trial. The incorporation of cognitive and behavioral strategies will promote increased adherence to exercise over the long term (Ellis et al., 2011). Information derived from this study could be easily translated into clinical practice guidelines and disseminated widely at relatively low cost within the VA Healthcare System and beyond.

The current proposal directly addresses a specific area of RR&D interest in that we have developed a computer-assisted rehabilitation strategy – specifically technology for remote real-time delivery of a physical activity program, primarily walking.

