### **3. PRELIMINARY STUDIES**

#### **3.1 TLC-WALK**

We have developed a novel automated telecommunications system for coaching and monitoring physical activity in real time which we are currently using in an HSR&D project with the aim of reducing sleep apnea severity. The system, the Telephone-Linked Computer-based system for Walking (TLC-WALK), provides a highly structured walking regimen with heart rate (HR) monitoring and real-time feedback. HR is collected from a chest strap and transmitted wirelessly to a smartphone and audio feedback is provided via a headset.

Each exercise session consists of three parts, a 5-minute warm-up phase, a walking or endurance phase, and a 5-minute cool-down phase. For the walking or endurance phase, TLC-WALK sets a target HR range for the participant to maintain for a minimum time while walking, which is set at 10 minutes in the beginning of the program. Each week, there is a minimum goal of completing three sessions. The entire length of the session and the total number of sessions required are both dependent on the ability of the participant to maintain the target HR. However, the session duration never exceeds 60 minutes (50 minutes of exercise plus 10 minutes of warm-up and cool-down stretches). The target HR range and/or the target minimum duration is increased at the end of each week as long as a participant is able to meet the target HR and duration goals for at least two sessions during the week. If a participant does not meet the target HR and duration goals during a given session, the system interactively compensates by increasing the duration of the walking phase and encouraging the participant to add more sessions to the weekly schedule.

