We have incorporated multiple counseling modules into TLC-WALK which are delivered during the cool-down phases as well as a relapse-prevention module which is delivered at the beginning of selected walking sessions. The strategies employed by TLC-WALK have a strong behavioral theoretical underpinning in social cognitive theory (Bandura, 1986) and the stages of change model, which is used to guide interventions for a number of health behaviors (e.g., smoking cessation, physical activity) in various settings (e.g., in communities and physicians' offices). These theories make use of several constructs aimed at changing ways of thinking (cognitive strategies) and increasing specific behaviors (behavioral strategies). We have also incorporated a cognitive training module which is delivered via the smartphone before the warm-up phase of the session.

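### Does the trial need a physical activity measure in both arms, when activity is recorded only inside TLC-WALK sessions?

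*Combined protocol and SAP*

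**What the plan says.** Section 1 states the purpose: "to conduct an RCT of a home-based physical activity intervention program" in patients with PD-MCI, with the hypothesis framed as less ADAS-Cog decline over 6 months than in the control arm. Section 4.5 names the ADAS-Cog alone, collected "at baseline, 6 months, 12 months, and 18 months at the Jamaica Plain campus of the VA Boston Healthcare System" by a blinded assessor. Section 4.7 compares the arms on the ADAS-Cog in a mixed model and contains no activity variable.

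Activity is recorded in one place. Section 3.1 says of TLC-WALK that "HR is collected from a chest strap and transmitted wirelessly to a smartphone", and the system sets weekly targets from heart rate and duration. The Significance section expects objective measures to represent how long and how hard subjects exercise, and adds that "these objective measures will be the basis for the progression and optimization of physical activity throughout the course of the trial". It names no instrument, schedule or arm.

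Controls receive exercise instruction in their first three weeks. Section 4.4.2 says: "There are a total of six topics (three related to stretching and three related to aerobic conditioning exercise) in this content area". Those topics stay available afterwards. Control subjects earn points for completing education sessions, which is not a record of exercise.

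**The concern.** Physical activity is what the intervention is meant to change, yet the plan could not report whether activity differed between the arms. The controls are taught aerobic exercise. The source trial's control arm, as summarised in Section 2.5.2, lists no exercise topic, but its 0.580 SD effect is carried into Section 4.8 without comment.

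The background seems to make the gap harder to excuse. Section 2.5.2 gives as a limitation of the source trial "the inability to adequately monitor the progression of physical activity and encourage adherence by telephone as originally planned", and says of the observational cohorts in its meta-analysis: "All of the studies used self-report of physical activity which lacks precision".

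What is at stake is interpretation. A null ADAS-Cog result could mean that walking does not slow decline, or that the two arms ended up about equally active. Those readings point to different next steps, and activity not recorded at 6 months cannot be recovered.

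**Working it through.** **1. The plan's own figure.** Inputs from Section 4.8: mean difference 2.16 points, effect size 0.580, 5% level (taken as two-sided), 90% power, 64 per group. Table 2 gives 95% intervals of -1.83 to 0.08 (n=48) and 0.20 to 2.39 (n=52).

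- SD per arm = (half-width / 1.96) × √n. Exercise: (0.955/1.96) × √48 = 3.38. Control: (1.095/1.96) × √52 = 4.03.
- Pooled SD = √[(47 × 3.38² + 51 × 4.03²)/98] = 3.73, and 2.16/3.73 = 0.579. The 0.580 reproduces.
- Two-sample t-test at 0.580: power 0.898 with 63 per group, 0.902 with 64, and 0.954 with 80 (all 160 analysed). The 64 per group reproduces.

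**2. What control exercise could do to power.** Suppose k of n controls gain the full source effect. The expected difference is then (1 − k/n) × 0.580.

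| Analysed per arm | Controls gaining full effect | Difference (SD) | Power |
|---|---|---|---|
| 64 | 0 | 0.580 | 0.902 |
| 64 | 9 | 0.498 | 0.799 |
| 80 | 0 | 0.580 | 0.954 |
| 80 | 9 | 0.515 | 0.899 |
| 80 | 19 | 0.442 | 0.794 |

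Expressed as a share of the effect lost, 20% leaves 0.464 SD, with power 0.740 (64 per arm) or 0.831 (80). A 30% loss leaves 0.406 SD, with power 0.625 or 0.723.

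The documents give no rate of control exercise and no benefit per exercising control, so every row other than the zero rows is hypothetical. The rows describe dilution, which would occur whether or not activity was measured. The cost of not measuring is a loss of explanation, and these figures do not size it.

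**3. What an added measure would deliver.** The 95% half-width for a standardised activity difference is t × √(2/n): 1.979 × √(2/64) = 0.350 SD, or 1.975 × √(2/80) = 0.312 SD. If separation were declared only when the interval excludes zero, a true activity difference of 0.35 SD would pass with probability 0.50 (64 per arm) or 0.59 (80). About half the time a real separation of that size would be reported as not shown.

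**4. Whether a positive result could then be credited to walking.** Section 3.1 says TLC-WALK also contains "a cognitive training module which is delivered via the smartphone before the warm-up phase of the session". Cognitive training is delivered with the walking in one arm only, so knowing that activity differed would still not isolate its effect on a cognitive scale.

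**5. Whether TLC-WALK is a stronger dose than the source programme.** Section 2.5.2 gives the source as 150 minutes a week in three 50-minute sessions. Section 3.1 starts the walking phase at 10 minutes, sets a minimum of three sessions a week, and caps exercise at 50 minutes per session. No numerical heart-rate target is given. The documents do not support calling TLC-WALK more intensive, and the direction of any departure from 0.580 is unknown.

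**The case for a change.** The strongest case for a change is that the Significance section speaks of objective measurement among subjects generally, and nothing carries this to the control arm. Session logs cover one arm, and only while a session is running. The supervised first TLC-WALK session follows assignment, so it is not a baseline. One common recording near 6 months would alter neither intervention and would let a null result be read with more confidence. The manual of operations mentioned in Section 4.2 might specify a measure, but it is not part of the public documents.

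Most of this stands as description. The Significance text promises more than Sections 4.5 and 4.7 deliver, and a common measure would be informative.

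It carries less weight as grounds for revision. The source-trial limitation quoted above concerns following progression and encouraging adherence, which real-time monitoring in TLC-WALK addresses; it does not commit the plan to measuring controls. The TLC-WALK logs can show whether that arm walked as prescribed, so a null result from poor uptake is partly distinguishable. Device recording would mean 160 recordings (320 with a baseline), some missing wear data, and the chance that wearing a device itself prompts activity. A questionnaire costs little, but subjects know their arm and could report a separation that did not occur; it is also the kind of measure that Section 2.5.2 criticises.

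**Conclusion.** No change follows. The gap is real but limited: activity outside TLC-WALK sessions, and at any time in the controls, will be unknown. The randomised ADAS-Cog comparison remains valid as a comparison of two programmes as delivered, which is the comparison that Sections 1 and 4.1 set up. The 90% power at 0.580 SD is correct as stated.

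The possible erosion of power, for example from 0.902 to 0.799 if 9 of 64 controls gained the full source effect, rests on a contamination rate that the documents do not give, and an activity measure would not reduce it. Such a measure would add explanatory value at moderate cost. It would not settle attribution, because cognitive training is bundled with the walking, and at these sample sizes it would estimate separation only to about ±0.31 to ±0.35 SD.

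Leaving it out is a fair trade-off, provided the report describes the contrast as TLC-WALK against health education and presents activity data as in-session data from one arm. An analyst would do that without an amendment.

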#### 2.2 **Cognitive Impairment in Parkinson's Disease**

Cognitive impairment is one of the most common and important nonmotor impairments of PD contributing to profound levels of disability. Variable degrees of cognitive impairment are common in the first 3 to 5 years following diagnosis of PD, most frequently revealing impairment in areas of attention-executive function, visuospatial ability, working memory, and verbal memory recall tasks (Copeland et al., 2013). The underlying mechanisms of cognitive impairment and dementia associated with PD are incompletely understood and no mechanism-based treatments are currently available. The present theoretical consensus postulates that both dysmetabolism of  $\alpha$ -synuclein and amyloid-protein and cholinergic deficits contribute to cognitive impairment in PD.

The average prevalence of dementia in PD is approximately 30% based on cross-sectional studies (Aarsland et al., 2005; Riedel et al., 2010). The 8-year cumulative prevalence, however, approaches a staggering 80 percent (Aarsland et al., 2003). Mean time to diagnosis of dementia was approximately 6 years.

MCI is also common in PD and frequently progresses to dementia. In a population-based study of an incident PD cohort, Pedersen and colleagues (Pedersen et al., 2013) reported that among patients with MCI almost half progressed to dementia. Uniform criteria of PD-MCI have recently been proposed to improve comparability between studies (Litvan et al., 2012).

Given the profound negative health and social consequences associated with the development of dementia, it is critical to identify interventions that effectively slow the decline of cognitive function to prolong

the time to onset of dementia. Rehabilitation programs for individuals with PD have been primarily aimed at improving motor function. Nonmotor complications, such as cognitive impairment, are less commonly treated using nonpharmacological approaches. In a recent review of cognitive impairment in PD, the authors conclude that urgent treatment of cognitive impairments is necessary to improve function, enhance quality of life (QOL), and reduce caregiver burden, health care costs and risk for nursing home admissions (Svenningsson et al., 2012).

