### **2.4 Cholinesterase Inhibitors to Improve Cognitive Function**

A recent Cochrane review assessed the efficacy, safety, and tolerability of cholinesterase inhibitors (donepezil, rivastigmine) in PDD (Rolinski et al., 2012) based on randomized placebo-controlled trials. Cholinesterase inhibitors lead to an improvement in cognitive function as measured by the ADAS-Cog (Dubois et al., 2007; Dubois et al., 2012; Emre et al., 2004; Ravina et al., 2005) (weighted mean difference, -2.72, 95% confidence interval [CI], -3.61 to -1.83,  $p < 0.001$ ). Those taking a cholinesterase inhibitor were more likely to experience an adverse event (odds ratio 1.64, 95% CI, 1.26 to 2.15,  $p < 0.001$ ) and to drop out (odds ratio 1.94, 95% CI, 1.33 to 2.84,  $p < 0.001$ ).

In the Express trial (Emre et al., 2004), rivastigmine was found to significantly improved cognitive function in persons with PD using the ADAS-Cog. Subsequent studies revealed that cognitive function improved across several domains including memory and executive function (Schmitt, Aarsland et al., 2010; Schmitt, Farlow et al., 2010) in a pattern indistinguishable from the response in AD.

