Data from functional MRI studies in normal aging and AD suggest that aerobic exercise improves the efficiency of neuronal activity in areas within the prefrontal cortex similarly affected in PD (Colcombe et al., 2004; Angevaren et al., 2008). Impairments in cognition in PD are associated with dysfunction of the basal ganglia circuitry and the frontal-cortical regions. The disruption of the nigro-striatal-thalamic-cortical circuitry that connects the striatum to the prefrontal cortex accounts for the impairments in executive function characteristic of PD (Dujardin et al., 2003). Recent studies provide preliminary evidence of the effectiveness of aerobic exercise in improving frontal lobe function. For example, a controlled study investigating the efficacy of aerobic exercise training in persons with PD revealed selective benefits in frontal lobe-mediated executive function (i.e., letter fluency test) (Cruise et al., 2011). Similarly, a non-randomized controlled trial investigating the effects of a 6-month aerobic exercise program in persons with PD revealed significant improvements in executive function in the intervention relative to control group (Tanaka et al., 2009). More research is needed to evaluate the benefits of exercise in improving cognition in PD.

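### Does relying on ADAS-Cog alone, with no separate executive-function test, leave a null result uninformative?

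*Combined protocol and SAP*

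**What the plan says.** The sections that define the trial's question agree. Section 1 hypothesises that intervention participants "will have less decline in this outcome over 6 months compared with those in the control arm", the outcome being the ADAS-Cog. Section 4.5 has a blinded staff member administer it at baseline, 6, 12 and 18 months and describes it so: "The scale consists of eleven items assessing memory, orientation, language, and praxis". Section 4.7 compares the arms on it with a mixed model, taking the 6-month contrast first. Section 4.8 sizes the trial on it. No second outcome or subscale analysis appears.

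The background is broader. Section 2.2 describes early cognitive impairment in PD as "most frequently revealing impairment in areas of attention-executive function, visuospatial ability, working memory, and verbal memory recall tasks". Section 2.5.2 adds: "Recent studies provide preliminary evidence of the effectiveness of aerobic exercise in improving frontal lobe function". It then describes two human studies, one reporting a benefit on letter fluency and the other, which was not randomised, on executive function.

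The background also supports the chosen scale. Section 2.4 says of PD dementia: "Cholinesterase inhibitors lead to an improvement in cognitive function as measured by the ADAS-Cog". Section 2.5.2 reports that the walking trial on which this design is based found an effect on "a comprehensive cognitive measure (ADAS-Cog) and a delayed recall task".

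**The concern.** Set the Section 4.5 summary beside the PD rationale and there seems to be a mismatch. The four areas listed for the scale include neither attention nor executive function, while the human PD exercise evidence on cognition is about executive function. The exercise evidence for the ADAS-Cog comes from people aged 50 or older with memory complaints, not from PD patients.

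If exercise in PD acts mainly on executive function, the ADAS-Cog could be null while a real benefit went unmeasured. A test not given at baseline cannot be recovered later. One short letter fluency test, tested only after the primary, looks like an inexpensive safeguard.

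**Working it through.** **1. Is the plan's own question coherent and correctly sized?**

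Inputs from Section 4.8: mean difference 2.16; exercise change -0.87 (-1.83 to 0.08), n = 48; control change 1.29 (0.20 to 2.39), n = 52; 90% power; 5% level. I assume that the intervals are 95% and the test two-sided.

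- SD, exercise: (0.08 + 1.83)/2 / 1.96 × √48 = 3.38.
- SD, control: (2.39 − 0.20)/2 / 1.96 × √52 = 4.03.
- Pooled SD: √[(47 × 3.38² + 51 × 4.03²)/98] = 3.73.
- Effect size: 2.16/3.73 = 0.579, against 0.580 stated.
- Sample size: 2 × (1.960 + 1.282)²/0.580² = 62.5, so 63 per arm by the normal approximation. The exact noncentral t gives 64 per arm, 128 in total, as stated.

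The hypothesis, data collection, analysis and sample size all concern the same scale. A null would be a null on the quantity that the trial set out to test.

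**2. Do the documents show that the scale misses executive change?**

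No. The premise rests on a one-sentence description of eleven items. Against it, Section 2.4 says that rivastigmine improved the ADAS-Cog in PD, and that later studies found gains extending to executive function as well as memory. By its title in the reference list, one of those studies evaluated the drug through ADAS-Cog items. This does not prove executive sensitivity: the evidence is from drug trials in dementia, and the other study cited there concerns executive function directly. But the point is open, and the plan's own text leans partly the other way. Section 2.2 also lists verbal memory recall, which overlaps the memory content of the scale. Section 2.5.2 argues for effects on general brain health as well as on specific circuits.

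**3. Is the public text complete on this point?**

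Perhaps not. The reference list contains a Stroop test manual, a verbal learning test and a 1968 paper on frontal lobe disease, none of them cited in the text. Section 4.6 speaks of quality checks on all measures although only one outcome is named. This is consistent with a condensed text, though it does not prove one.

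**4. What would an added letter fluency test deliver?**

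The documents give no SD or expected effect for it, so the units are SDs of its change score, without baseline adjustment. The 95% half-width is t(0.975, 2n − 2) × √(2/n); detectable difference and power come from the noncentral t.

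| | 64 per arm (Section 4.8) | 80 per arm (all 160) |
|---|---|---|
| 95% CI half-width | 1.979 × 0.177 = 0.350 | 1.975 × 0.158 = 0.312 |
| Difference detectable at 80% power | 0.50 | 0.45 |
| Power at 0.3 SD | 39% | 47% |
| Observed difference below which the CI excludes 0.580 | 0.580 − 0.350 = 0.230 | 0.580 − 0.312 = 0.268 |

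An observed 0.20 SD at 64 per arm gives 0.20 ± 0.35, or -0.15 to 0.55, which is compatible with no effect and with a moderate one. The 0.580 yardstick is itself borrowed from another scale in a trial that was not in PD.

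If letter fluency may be tested only after a significant ADAS-Cog result, the chance of a formal claim on it after a null primary is zero by construction. That is the one situation the addition is meant to inform.

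**5. What would it cost?**

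160 × 4 visits = 640 administrations. At an assumed 5 minutes each, 640 × 5/60 = 53 assessor hours (32 at 3 minutes, 107 at 10), plus up to 640 more forms for double entry. Training and scoring time are not counted.

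**The case for a change.** The best case for the addition is that it would not touch the primary. Tested in sequence, letter fluency leaves the ADAS-Cog its full 5% level and its power of about 90%; an even split of alpha would lower that power at 64 per arm from 0.907 to 0.851 (normal approximation). The visits and the blinded assessor are already in place. If exercise had no effect on the ADAS-Cog but a true executive effect as large as 0.58 SD, the letter fluency interval at 64 per arm would exclude zero about 90% of the time. A descriptive estimate of that kind would have value, and the text describes no PD exercise study with an ADAS-Cog effect.

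All of this stands as an argument that the test could be useful. It does not show that the plan is wrong. The value depends on a large executive effect, for which the documents offer two studies that they themselves call preliminary; at 0.3 SD the power is below one half. One fluency test does not cover the executive domain, nor visuospatial ability or working memory. A gain could also come from the cognitive training module in Section 3.1 rather than from walking. That ambiguity applies to the ADAS-Cog too, but it weakens any reading of letter fluency as evidence on exercise. A wish for one more secondary outcome could be raised against almost any trial with a single outcome.

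**Conclusion.** The concern does not hold. Followed as written, the plan gives a sound answer to the question it poses, on a scale that its own background supports and with a sample size that reproduces. The absence of a separate executive estimate is a limit on what else the trial can learn. It is neither a contradiction nor a bias, and it changes no primary result. The size of the supposed risk cannot be derived from the documents.

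This conclusion rests on the public text, a two-sided 5% test, and 64 to 80 analysed per arm (no dropout rate is stated; 128/160 would correspond to 20% loss). It does not rest on the ADAS-Cog being sensitive to executive change, which the documents leave open. A null should be read as a null on the ADAS-Cog, which is how Section 1 frames the hypothesis.
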